### **3.3.6 Restrictions**

Not applicable

## **3.4 Treatments**

### **3.4.1 Investigational products**

#### **3.4.1.1 Identity of investigational product and comparators**

Generic name: esomeprazole

Dosage form: tablet

Strength: 20 mg

Manufacturer's name: AstraZeneca Pharmaceutical Production

Type of packaging: plastic bottle

Run-in period: 100 tablets/bottle, white label

5-year study period: 100 tablets/bottle, white label

5-year study period increased dose: 100 tablets/bottle, white label

Healing dose/ dose adjustment: 100 tablets/bottle, white label

5 to 10-year study period: 100 tablets/bottle, white label

### 3.4.1.2 Labelling

**Note:** Only one label will be used from January 2007 and onwards. This label the “**5 to 10-year study period**” label will replace the “5-year study period”, “5-year study period increased dose” and “Healing dose/ dose adjustment” label.

#### **5 to 10-year study period**

AstraZeneca

100 tablets esomeprazole 20 mg, oral

Study/order ref.: SH-NEG-0003-XXX

Randomisation code: (to be filled in by hospital staff)

E-code: (to be filled in by hospital staff)

For the treatment of gastroesophageal reflux disease

Take ..... Tablet/tablets in the morning and ..... tablet/tablets in the evening with water

Prescribed by: Dr: (to be filled in by hospital staff)

Visit no: (to be filled in by hospital staff)

Visit date: (to be filled in by hospital staff)

Expiry date: YYYY-MM-DD

For clinical study use only

Store at room temperature (below 25 °C)

Keep out of reach of children

(LOTUS)

### 3.4.1.3 Storage

All investigational products must be kept in a secure place under appropriate storage conditions.

### 3.4.1.4 Accountability

The amounts of investigational drug that is dispensed and returned will be recorded in the subject specific CRF. The unused investigational drug will be returned to AstraZeneca and destroyed according to routine procedures.

### **3.4.2 Doses and treatment regimens**

The medication arm of the study design includes the following:

- esomeprazole
- oral administration
- the start dose is 20 mg once daily and may be adjusted not to exceed 40 mg total daily dose and be swallowed together with a glass of water.

The surgical arm of the study design includes the following:

The surgical procedure is laparoscopic fundoplication. The surgical procedure to be used is laparoscopic total fundoplication and reconstruction of the hiatus. A per-operative record should be filled in and sent by the monitor to AstraZeneca R&D Mölndal for datahandling. The procedure should be done by or supervised by an experienced surgeon. Surgery should be performed within three months of randomization. The subject is allowed to be treated with esomeprazole 20 mg o.d or 40 mg o.d awaiting the surgery.

### **3.4.3 Method of assigning subjects to treatment groups**

Individual treatment codes, indicating the treatment allocation for each randomized subject, will be provided by AstraZeneca.

The subjects will be randomized into either esomeprazole or anti-reflux surgery.

Subject eligibility will be established before treatment randomization. Subjects will be randomized strictly sequentially. If a subject discontinues from the study, the randomization number will not be reused, and the subject will not be allowed to re-enter the study.

### **3.4.4 Blinding and procedures for breaking the blind**

#### **3.4.4.1 Methods for ensuring blinding**

Not applicable, as this is an open study. See Section [3.2](#).

#### **3.4.4.2 Methods for breaking the blind**

Not applicable

### **3.4.5 Pre-study, concomitant and post-study treatment(s)**

Subjects entering this study have most likely been on long-term treatment with various anti-acid secretion therapy (i.e. PPI, H2RA). During the 12 week run-in period the subject must undergo the “Investigational week” including endoscopy with biopsy sampling, 24 hr pH-metry, manometry, SAP and laboratory measurements. In order to get relevant pH measurements the study medication (esomeprazole 40 mg o.d.) must be stopped at least 7 consecutive days before the 24 hr pH-metry at visit 3. Subjects randomized to anti-reflux surgery should be treated with

esomeprazole (20 mg o.d. to 40 mg daily) before surgery (within three months from randomization).

Motility activators (prokinetic drugs) e.g. metoclopramide are allowed for operated subjects between visit 5 and visit 6 for treatment of post-operative intestinal paralysis.

In case of an ulceration/erosion in the fundoplication within 3 months post surgery, subjects are allowed to be treated with esomeprazole 40 mg o.d. for 2-12 weeks. Subjects in the surgical arm are instructed to take antacid/alginate medication if they experience dyspeptic symptoms after surgery. If the subject has need for additional medication he/she shall contact the investigator who may dispense 1 bottle of esomeprazole 20 mg to be taken on demand, not more than one tablet daily. Unused medication is to be returned on the following visit (visit 7) and drug accountability is to be recorded in the CRF. After visit 7 no such medication is allowed. Subjects in the surgical arm, who develop a gastric or duodenal ulcer due to intermittent usage of NSAID are allowed to be treated with esomeprazole 40 mg o.d. for 2 weeks.

Concerning *Hp* eradication please see Section 3.1.

Antacids and alginates are allowed during the study.

Other medication which is considered necessary for the subject's safety and well being may be given at the discretion of the investigator(s). The administration of all medication (including investigational products, antacids and alginates) must be recorded in the appropriate sections of the case report form (CRF).

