**Need for medical treatment for control of symptoms from reflux disease:**

In order to allow for a stringent assessment of treatment failure ask the following question:

*“Do you have sufficient control of your heartburn and acid regurgitation?”*

If the answer is **No**, continue with:

*”Do you need other regular drug treatment to control your symptoms?”*

If the answer to this question is **Yes** the subject has to be classified as a **treatment failure and will be withdrawn**.

Furthermore, the subject will also be regarded as a **treatment failure** if the following occurs;

- Post-operative - post-fundoplication complaints requiring further medical actions to control symptom burden.
- Per-operative death
- Post-operative death within 30 days after surgery
- Dysphagia requiring further treatment. In case of esophageal stenosis, one dilatation is allowed.

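### On-demand esomeprazole permitted after surgery (Section 3.4.5) can also count as treatment failure under the post-operative complaints criterion (synopsis, Sections 4.1 and 6.2.2), and the protocol does not say which applies

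*Protocol*

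**What the plan says.** **Permission.** Protocol Section 3.4.5 states: "Subjects in the surgical arm are instructed to take antacid/alginate medication if they experience dyspeptic symptoms after surgery". A subject who needs more than that contacts the investigator, "who may dispense 1 bottle of esomeprazole 20 mg to be taken on demand, not more than one tablet daily". Leftover tablets are handed back at visit 7 and accounted for in the case report form (CRF), and "After visit 7 no such medication is allowed". The list of prohibited drugs that follows refers back to this section as an exception to the ban on proton pump inhibitors for the surgical arm.

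The same section contains a second permission: "In case of an ulceration/erosion in the fundoplication within 3 months post surgery, subjects are allowed to be treated" with esomeprazole for 2 to 12 weeks.

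**Failure definition.** In the surgical arm, the synopsis, Section 4.1 and Section 6.2.2 give two routes to failure that matter here. One is a two-step interview. It asks whether heartburn and acid regurgitation are sufficiently controlled and, if not, "Do you need other regular drug treatment to control your symptoms". The other is a list of further events, the first of which is "Post-operative - post-fundoplication complaints requiring further medical actions to control symptom burden". None of the three places limits that item in time or mentions Section 3.4.5.

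**Consequence.** Section 3.3.5.1 lists being classed as a treatment failure among the reasons for discontinuing a subject.

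**The concern.** Take a subject with complaints after the fundoplication that antacids do not settle, to whom the investigator gives esomeprazole before visit 7. Under Section 3.4.5 this is permitted care and the subject goes on. Under the complaints item, a post-operative complaint has required a further medical action, so the subject has failed and may be discontinued. The protocol leaves the choice to the person at the site, who knows the allocation.

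The question arises in one arm only. Section 4.3.2.1 counts time from the start of treatment, so the ambiguity also falls early in the surgical time-to-failure curve. If sites resolve it differently, the surgical failure rate partly reflects how sites read the protocol. It cannot be fully repaired later: under Section 3.1, discontinued subjects who have not withdrawn consent are followed only by telephone, at 5 and 10 years.

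**Working it through.** **1. The rules side by side**

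| | Section 3.4.5, on-demand supply | Complaints item (synopsis, 4.1, 6.2.2) |
|---|---|---|
| Trigger | dyspeptic symptoms after surgery, not held by antacid or alginate | post-operative or post-fundoplication complaints |
| Action | investigator dispenses esomeprazole | a further medical action (not defined) |
| Time limit | up to visit 7 | none |
| Result | drug returned at visit 7, so the subject continues | treatment failure, a reason for discontinuation |

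The triggers and actions overlap and the results exclude each other. The list containing the complaints item does write in an exception elsewhere, allowing a single dilatation for stenosis. It has none for medication under Section 3.4.5.

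**2. Length of the overlap.** Surgery takes place within 3 months of randomization and Table 1 puts visit 7 at 6 months, so the window is about 3 to 6 months. Section 3.4.1.1 gives 100 tablets per bottle. At one tablet a day at most, one bottle covers 100 days of daily use if the window is long enough.

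**3. The plan's own precision.** Section 6.1 assumes at least 70% success at 5 years in both arms, 275 subjects per arm, and a difference known to within 8 points with 95% probability.

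Half-width = 1.96 × √(2 × 0.70 × 0.30 / 275) = 0.0766, or 7.7 points. With a continuity correction of 1/275 it is 8.0 points. The stated 8 reproduces and serves as the yardstick.

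**4. Effect of reclassifying users.** Let *q* be the share of the 275 surgical subjects who use the permitted supply. The protocol gives no value, so 5–20% is an assumption. Suppose success is 70% in both arms when users are not counted as failures.

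- If use is independent of later failure, surgical success with users counted as failures is 0.70 × (1 − *q*), a shift of 0.70*q*.
- If every user would otherwise have succeeded, it is 0.70 − *q*, a shift of *q*. This is the upper bound.

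The chance of a significant two-sided 5% difference uses a two-proportion approximation at 5 years in place of the log-rank test. Worked for *q* = 10% under independence:

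- Mean success is 0.665 and the null standard error is √(2 × 0.665 × 0.335 / 275) = 0.0402, so the critical difference is 1.96 × 0.0402 = 0.0789.
- The standard error under the alternative is √((0.70 × 0.30 + 0.63 × 0.37) / 275) = 0.0401.
- Φ((0.070 − 0.0789) / 0.0401) = 0.41.

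| *q* | Users | Success, independent | Shift (points) | Extra failures | Chance of significance | Success, upper bound | Chance of significance |
|---|---|---|---|---|---|---|---|
| 5% | 14 | 66.5% | 3.5 | 10 | 0.14 | 65% | 0.24 |
| 10% | 28 | 63.0% | 7.0 | 19 | 0.41 | 60% | 0.69 |
| 15% | 41 | 59.5% | 10.5 | 29 | 0.73 | 55% | 0.955 |
| 20% | 55 | 56.0% | 14.0 | 39 | 0.93 | 50% | 0.998 |

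The shift equals 8 points at *q* = 0.08 / 0.70 = 11.4% under independence, and at 8% in the upper-bound case.

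**The case against.** The best answer is that Section 3.4.5 is a specific, time-limited exception to a general rule. Much supports this. The prohibited-drug list points to it. Discontinuation for prohibited drugs requires continuous need or intake (Section 3.3.5.1). Table 1 records compliance at visit 6 for surgical subjects receiving esomeprazole. Section 3.1 lets satisfied surgical subjects with temporary symptoms take antacids and continue, so a further medical action cannot mean any medication at all.

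This shows that the drug is allowed and that such subjects were expected to continue. It does not show how they are classified, because every one of these exceptions concerns medication or continuation and none appears in the endpoint definition. Antacid use does not settle the matter either, since the on-demand supply is by construction the step beyond antacids.

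Three stronger readings are tempting, and the documents do not support them:

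- **That the two-step interview is contradicted as well.** Its second question concerns regular drug treatment for uncontrolled heartburn and regurgitation. On-demand use of one bottle for dyspeptic symptoms need not meet it.
- **That the ulceration or erosion course conflicts in the same way.** Its trigger is a lesion. It meets the complaints item only where complaints prompt the treatment.
- **That the permission hides surgical failures for good.** The on-demand supply ends at visit 7. A subject with continuing need then faces the failure questions, so that failure is delayed by months. The classification differs lastingly only for subjects whose symptoms settle.

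It is also fair that sensitivity analyses usually belong in a statistical analysis plan. The definition itself cannot wait for one, because sites classify and discontinue subjects from the protocol.

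**Conclusion.** The concern holds for the on-demand esomeprazole in Section 3.4.5 set against the single item on post-operative and post-fundoplication complaints. Those two texts allow the same event, between surgery and visit 7, to be permitted care or a primary-endpoint failure. That conclusion rests on the wording alone.

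The size is conditional. With assumed use of 5–20%, independent of later failure, surgical 5-year success moves by 3.5 to 14 points, reaching the stated 8-point precision at about 11% use. A reader might instead infer a shift of 5 to 20 points, with 8% use enough to match the precision. That holds only if every user would otherwise have succeeded, which nothing in the protocol supports. The base of 275 is also slightly generous, because Section 6.2.1 removes subjects who refuse the operation from the intention-to-treat analysis.

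**What to change.** Section 3.4.5 must be reconciled with the synopsis, Section 4.1 and Section 6.2.2, so that esomeprazole given after surgery under Section 3.4.5 has one stated endpoint classification. Which classification applies is for the clinical team. A sentence in the failure definition and a cross-reference in Section 3.4.5 are enough. The same sentence should cover an ulceration or erosion course prompted by complaints.

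In the analysis, flag every surgical subject who received this medication, using the CRF medication record that Section 3.4.5 already requires. Report the primary comparison with these subjects classified each way. Where a site has already discontinued such a subject as a failure, the alternative analysis can only censor at discontinuation, and the report should give the number affected.

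The cost is a short text change and one extra sensitivity analysis, with no new data collection.

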#### Not allowed concomitant medication

The following drugs are not allowed during the course of the study. NB including OTC drugs.

- per oral anticholinergics and other drugs having anticholinergic co-effects such as tricyclic and tetracyclic antidepressive drugs
- motility activators (prokinetic drugs) - except for operated subjects between visit 5 and visit 6 for treatment of post-operative intestinal paralysis.
- prostaglandin analogues
- NSAIDs (except for intermittent usage e.g. 2 weeks twice yearly, prn  $\leq$  3 days per week)
- ASA (except for 165 mg less daily for cardiovascular prophylaxis)
- anticoagulants are not allowed 2 weeks prior to endoscopy
- PPI (other than study medication/for surgical arm please see above in Section 3.4.5)

- H2RA
- *Hp* eradication therapy during the run-in period

### 3.4.6 Treatment compliance

Subjects will be instructed to return all unused study drugs at each visit. Returned tablets will be calculated and documented in the CRF.

## 4. STUDY MEASUREMENTS AND ENDPOINTS

### 4.1 Primary endpoint

The primary endpoint of the study is time to treatment failure, defined as

- Time to treatment failure where **treatment failure** is defined as;

a/ In the medical arm:

**Need for treatment other than esomeprazole for control of symptoms of reflux disease:**

In order to allow for a stringent assessment of treatment failure ask the following the question:

*“Do you have sufficient control of your heartburn and acid regurgitation?”*

If the answer is **No**, continue with:

*“Do you need other regular drug treatment to control your symptoms?”*

If the answer to this question is **Yes** and the dose of esomeprazole is 20 mg once daily, then the dose is to be increased to 40 mg once daily. The subject will be treated with the increased dosage for 8 weeks before a second dose adjustment can be made.

If the answer to this question is **Yes** and the dose is esomeprazole 40 mg once daily, then the dose is to be changed to 20 mg twice daily. The subject will be treated with the changed dosage for 8 weeks before being classified as a treatment failure if sufficient symptom control has not been achieved.

If the answer to this question is **Yes** and the dose is 20 mg twice daily, then the subject is a **treatment failure and will be withdrawn.**

b/ In the surgical arm:

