- All serious adverse events and those adverse events causing premature discontinuation of study drug and/or study will be recorded at each visit except visit 1 and 5 (surgery visit).

During the 10-year study period subjects in both treatment arms having (moderate-severe) recurrent GERD symptoms on at least **3 consecutive days** will be instructed to contact the clinic. The subject will be asked to answer the questions regarding treatment failure and follow the instructions for each treatment arm. In case of dose adjustments, the increased dosage must be taken for 8 weeks before a second dose adjustment is made. A 24 hr pH metry and SAP should be made prior to dose adjustment (only applicable to an adjustment to a higher dose). If the subject is symptom-free and satisfied after this treatment period with an increased dose, a reduction to the previous lower dose should be aimed at. At least one attempt to return to the previous lower dose should be made. After two periods of dose increase due to recurrence of symptoms, the investigator can decide which dose is required to maintain symptoms under control for the remaining study period, but the dose cannot exceed 40 mg o.d. or 20 mg b.i.d.

[figure not shown]
In case of subjects who are satisfied with their treatment, but with temporarily (at least **3 consecutive days**) moderate-severe GERD symptoms, the subject will be offered an endoscopy and:

- Subjects in the medical arm will then receive treatment with esomeprazole 40 mg o.d. for 2-12 weeks according to endoscopic findings and symptomatology. After treatment the subject in the medical arm will continue the study with esomeprazole at a dose which is required to maintain symptoms under control but does not exceed 40 mg daily.
- Subjects in the surgical arm are allowed to have symptomatic treatment (antacids) and will continue the study.

Visits 5 and 6 are only relevant to subjects randomized to surgery.

Interim analyses are planned 3 years (visit 12) and 5 years (visit 16) after last subject randomized (medical arm) or operated (surgical arm) on, to evaluate efficacy and tolerability.

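### The protocol gives two non-identical tests for primary-endpoint failure in a medical-arm subject on esomeprazole 20 mg twice daily

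*Protocol*

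**What the plan says.** Failure in the medical arm rests on two questions. The first is "Do you have sufficient control of your heartburn and acid regurgitation"; only a No leads to the second, "Do you need other regular drug treatment to control your symptoms". A Yes to the second moves the subject up a dose ladder whose last step is 20 mg twice daily. Two sentences then govern failure at that step:

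- **Test A** closes the paragraph on subjects coming from 40 mg once daily. The subject is "treated with the changed dosage for 8 weeks before being classified as a treatment failure if sufficient symptom control has not been achieved".
- **Test B** is the next paragraph. It starts from a Yes to the second question, "and the dose is 20 mg twice daily, then the subject is a" treatment failure, to be withdrawn.

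Both stand in Section 4.1 and are repeated in the synopsis and Section 6.2.2. Section 3.3.5.1 lists classification as a treatment failure among the reasons for discontinuation. Section 6.2.3 censors subjects who discontinue for any other reason.

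Section 3.1 covers moderate to severe reflux symptoms lasting at least three days in a row. For recurrent symptoms, "The subject will be asked to answer the questions regarding treatment failure and follow the instructions for each treatment arm". For subjects described as satisfied whose symptoms are temporary, an endoscopy is offered and "Subjects in the medical arm will then receive treatment with esomeprazole 40 mg o.d. for 2-12 weeks according to endoscopic findings and symptomatology", after which they continue in the study.

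**The concern.** Test A turns on symptom control, which is the content of the first question, and on eight weeks having passed. Test B turns on the answer to the second question and names no period. They are different criteria for the same state, and no passage says which governs or how they combine.

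This is the primary event definition. Sites apply it at open-label visits, and a subject classified as a failure is withdrawn. Two sites following the protocol in good faith could record the same subject as an event and as a continuing subject. If that continuing subject later leaves for a reason not classified as failure, Section 6.2.3 makes the record a censored one. A rule written later for the analysis cannot fully repair this, because a subject withdrawn under one reading has no further study visits. Section 3.1 provides only telephone follow-up, at 5 and 10 years.

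**Working it through.** **The plan's own figure.** Inputs from Section 6.1: 275 subjects per arm, success of at least 70% in both, and a difference known to within 8 points with 95% probability.

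Half-width = 1.96 × √(2 × 0.70 × 0.30 / 275) = 1.96 × 0.0391 = 0.0766, or 7.66 points. This agrees with the stated 8, and this concern does not affect it.

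**The two tests applied literally** to a subject on 20 mg twice daily:

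| Time on dose | Question 1 (control) | Question 2 (other drug) | Test A | Test B |
|---|---|---|---|---|
| under 8 weeks | Yes | not asked | no failure | no failure |
| under 8 weeks | No | No | no failure | no failure |
| under 8 weeks | No | Yes | not yet | **failure** |
| 8 weeks or more | Yes | not asked | no failure | no failure |
| 8 weeks or more | No | No | **failure** | no failure |
| 8 weeks or more | No | Yes | failure | failure |

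The tests disagree in two of the six states.

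- *No/No at 8 weeks or later.* Event status differs: failure under A, not under B.
- *No/Yes before 8 weeks.* B records a failure at once and A waits. If control is still lacking at week 8, the failure date differs by at most 8 × 7 = 56 days, which is 56/1826 = 3.1% of 5 years or 56/3652 = 1.5% of 10 years. If control has been regained by week 8, the subject is a failure under B only, so status differs as well.

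**Size.** One subject whose status changes moves the medical-arm proportion by 1/275 = 0.36 points. The documents give no frequency for either discordant state. Purely as an assumption, suppose 1%, 2% or 5% of the arm ended in the No/No state:

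- 0.01 × 275 = 2.75, about 3 subjects, 1 point
- 0.02 × 275 = 5.5, about 6 subjects, 2 points
- 0.05 × 275 = 13.75, about 14 subjects, 5 points

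These compare with a half-width of 7.66 points.

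**Section 3.1 beside Section 4.1.** The two routes in Section 3.1 share the same symptom severity and minimum duration. They are separated by whether symptoms count as recurrent or temporary and by whether the subject is satisfied. Section 3.1 does not say that *satisfied* means a Yes to the first failure question, so a site could send the same subject on 20 mg twice daily either way. Nor does it say how the 2-12 week course at 40 mg once daily applies to someone already on 20 mg twice daily.

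**The case against.** The best defence is to read Section 4.1 in sequence. The definition is headed by the need for a treatment other than esomeprazole, and a subject who answers No/No has no such need. On that view the eight-week sentence says when classification may take place and the following paragraph says how, with both questions put again after eight weeks. This would remove most of the conflict. It is a reasonable reading, but the protocol does not state it in any of the three places. Test A names its own criterion, and Test B carries no waiting period.

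Several stronger readings are tempting, and the documents do not support them.

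- *Section 3.1 keeps failing subjects in the study.* It sends recurrent symptoms to the failure questions. The 2-12 week course is for satisfied subjects with temporary symptoms, and the footnotes to Tables 1 and 2 treat the healing dose separately from dose adjustment. It therefore does not contradict the eight-week period, and no restart of the failure sequence is stated.
- *The step-down instruction is impossible after 20 mg twice daily.* The instruction that "a reduction to the previous lower dose should be aimed at" follows an increased dose. Section 4.1 calls the move to 20 mg twice daily a change, not an increase.
- *Investigator choice overrides Section 4.1.* The sentence that "the investigator can decide which dose is required to maintain symptoms under control for the remaining study period" concerns a dose that keeps symptoms controlled. A subject who answers No then Yes is not controlled, and nothing there suspends Section 4.1.
- *The ambiguity favours the sponsor's arm.* Counting No/No subjects as failures would add failures to that arm, and Test B can bring failures forward. The surgical definition also has elements of judgement, such as post-fundoplication complaints needing further medical action.

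**Conclusion.** The point holds for the two tests on 20 mg twice daily in the synopsis, Section 4.1 and Section 6.2.2. Read literally, they disagree in two of six answer states. One changes event status. The other changes the failure date by up to 56 days, or status if control returns by week 8. The exact effect is 0.36 points per subject whose status changes. The 1 to 5 point range rests on an assumed 1% to 5% of the arm and is illustration only. No direction of bias is claimed.

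In Section 3.1 only two secondary gaps remain: the undefined word *satisfied* and the silence on subjects already on 20 mg twice daily. The correction is still warranted because the conflict lies in the primary event definition, leads to withdrawal, and is cheap to remove.

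**What to change.** The sponsor should reconcile the two sentences into one failure test, worded identically in the synopsis, Section 4.1 and Section 6.2.2. It should state which answers count for a subject on 20 mg twice daily and whether the eight weeks must have passed. Section 3.1 should then be reconciled with that test by linking *satisfied* to the failure questions and saying how the 2-12 week course relates to a subject already on 20 mg twice daily. Which dose or withdrawal rule stands is for the sponsor to decide.

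The primary endpoint should also be analysed under the other reading as a sensitivity analysis, as far as the recorded answers, doses and dates allow. It will be incomplete for subjects already withdrawn under one reading.

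The cost is amendment wording, a derivation rule and one additional analysis. No extra visits are needed, and no new data if answers, doses and dates are already recorded.
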